Aim 3: To explore the effect of changes in theoretically important variables that may either moderate or mediate the effect of *SC+BFI* on BF and infant outcomes. We include hypothesized non-program factors (see Figure 1) that may moderate treatment efforts.

Aim 4: To explore community- and policy-level factors that may impact the sustainability of an incentive-based intervention with corporate representatives and insurance companies.

Aim 5: To track the intervention and medical costs for cost-effectiveness analyses.

- 4.2 The primary outcome is the BF continuation rate at 6-month postpartum. We hypothesize that the isolated effect of monthly incentives contingent on BF in *SC+BFI* will increase BF rates by 25% at 6-month compared to *SC*. The exploratory outcome is the BF continuation rate at 12-month postpartum. We will hypothesize that *SC+BFI* will increase the BF rate at 12-month, compared to *SC*.

We hypothesize that compared to the *SC* condition, the *SC+BFI* condition will have significantly lower infant weight gain and incidents of ER visits for infants at 3-month postpartum. We hypothesize that participants in *SC+BFI* would evidence greater increases in the motivation and self-efficacy, which, in turn, will account for between-group differences in outcomes.

5.0 Background/Literature Review/Rationale for the Study:

- 5.1 **Background:** Disparities in the health outcomes for mothers and their children exist due to low BF rates. WIC-eligible mothers are identified as at risk for early cessation of BF. Early cessation of BF leads to multiple health risks including increase in mortality and infectious diseases among infants and postpartum health issues. Several promising approaches exist to increase BF duration, including home-based professional and peer lactation support and financial incentives contingent on BF. However, these approaches have never established their efficacy to increase BF duration among low-income mothers.

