Differences between the study arms are that Standard Care receives compensations at the end of 6 month based on the number of completed home visitations (\$40/home visit) and Standard Care + BFI receives compensations at every home visit appointment if they are breastfeeding. The compensation for Standard Care + BFI is in an escalating schedule in which the first home visitation receives \$20 increasing by \$10 at every month up to \$70 if they demonstrate breastfeeding every month. Participants in Standard Care + BFI also receive \$50 per selection of full breastfeeding food package at WIC, potentially at baseline, 3, and 6 months postpartum.

- 10.3** Standard Care BF Support (WIC support + home-based individual support; Standard Care[SC]). Participants in SC will receive standard BF services from the WIC program, receive education on family nutrition, monitor their monthly nutritional habit, and be asked to participate in periodic assessments (1-, 3-, 6-, 9-, and 12-month postpartum). Combined institutional and home-based individual BF support by WIC and home-visiting lactation counselors has been already available in the community for Hispanic mothers as the standard of care model. Each periodic assessment will take approximately 30 minutes to complete.

WIC support component: Standard services from WIC will include on-site lactation consultation, bilingual peer counseling, peer support meetings, free breast pump, and enhanced food package for BF mothers. On-site lactation consultation, bilingual peer counseling, and peer support meetings occur once a week in each WIC office. Free breast pumps are given to WIC participants who have not had the benefit by the time they enroll into WIC. Enhanced food packages for BF mothers are distributed to WIC participants every three months.

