Standard Care + Breastfeeding Incentives (SC+BFI). Participants in *SC+BFI* will receive all WIC usual care elements the *SC* group receives, plus (the only element that is different between groups) an escalating amount of monthly financial incentives contingent on observed BF and that incentives will be delivered immediately upon verified BF at each month. This will isolate the component of contingent incentives on BF which is hypothesized to produce the largest effect on continued BF rates. Blinded RA will ask participants to demonstrate BF and provide individual support to praise efforts to continue BF and problem-solve BF issues.

Contingent incentive component: The incentive amount was \$20.00 at the end of the first month and increased by \$10.00 every month until the end of 6 months. The maximum potential earning is \$270.00. The initial incentive value of \$20 was determined in the pilot study based on inputs from WIC-receiving Puerto Rican mothers as the minimum amount of monthly incentives that would motivate them to breastfeed (not to substitute for compensation from work outside of home). An escalating schedule of monthly incentives was employed based on previous incentive-based interventions to encourage continuous abstinence from substance use. A participant who successfully demonstrates BF receives the incentive amount on a pre-paid credit card at the end of each month. If a participant misses an appointment or does not demonstrate BF, she will not receive the incentive. The rest of the procedure will be the same as for *SC*. We will also provide bonus incentives of \$50 to mothers who selected full BF food package from WIC at baseline, 3 months and 6 months postpartum. Selection of the WIC food package will be verified through WIC.

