- 10.4 Assessment.** All participants in both groups will be asked to complete periodic assessments at 1-, 3-, 6-, 9-, and 12-month postpartum intervals either at home or by phone. Assessments at 1, 3, and 6-month postpartum will be conducted by phone one week prior to home visit appointments and those at 9 and 12-month postpartum will be conducted in person. An RA will call a participant and make an appointment a week prior to the scheduled assessment date. The pilot study had the 97% follow-up rate at 6-month postpartum with this approach. Research measures for each timepoint is shown below. When a participant stops BF, she will be asked to explain the psychosocial or medical reasons of stopping BF, such as return to work, workplace policy on pumping, and lack of social support. Appointment cards will be given to participants for future appointments.
- 10.5 Payments.** Participants in *SC+BFI* will receive dollar amount incentives on a pre-paid credit card for breastfeeding. This type of system functions just like a Master Card and allows remote reloading. This system has been feasibly and effectively used by clinical populations. Un-blinded Project Coordinator will credit a dollar amount remotely on a Master Card for each participant. Participants in *SC* will receive a lump sum payment in form of retail gift cards at the end of 6 months based on the number of completed home visitations. The lump sum will be calculated after 6th month home visitation, and unblinded staff will notify the participant that the payment is ready for pick-up at the Temple University College of Public Health. All participants will receive retail gift cards for completing periodic assessments. Gift cards will be delivered in person on the day of in-person assessments, and at the next home visitation for phone-based assessments that are completed prior to the upcoming home visitation appointment. All participants will receive a gift basket at the 12-month visit as well.
- 10.6** Data source includes validated instruments for interview questions, breastfeeding observation records, and biological data and samples.

10.7 Description of data to be collected at each timepoint.

Screening/First home visitation:

Questionnaires to complete with staff between now and at the first home-based research assessment include:

Questionnaires	Description	When administered
Locator form	Participant contact information and emergency contacts	At the hospital floor

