- Anal swab from infants: Swabs from Zymo Research Corporation will be used to take a rectal swab from infants by research staff. Anal swabs will not go beyond the rectum area for sampling. The specific method will follow the noninvasive method of anal swab sampling defined by WHO (i.e., “Insert the swab tip just past the anal sphincter and rotate gently. Withdraw the swab and examine to ensure that the cotton tip is stained with faeces. Place the swab in a sterile tube/container containing the appropriate transport medium.”).²⁸ The anal swab will be used for examining microbiome composition and will not be used for genetic testing.

Monthly home visitations:

Interview questions include:

Questionnaires	Description
Daily log for pumping	Calendar on pumping patterns
Daily log for infant feeding	Calendar on feeding patterns
Daily log for moms eating	Calendar on moms’ eating pattern
Barriers against breastfeeding	Barriers to problem solve to continue breastfeeding
Maternal/infant health survey	Recent medical events for moms and infants
Tobacco, alcohol, caffeine, marijuana use past 7-day	Recent use of licit substances
Household structure	Total number of smokers living with the participant
Menstrual cycle	Questions about the last menstrual period

- Breastfeeding observation (LATCH): Identify BF behavior: Audible swallowing, regular suck/swallow/breathe pattern, or visible milk in the infant's mouth. For pumping, observed pumping combined with observed resulting milk being fed to the infant.
- Maternal weight measure: Measured with a portable Health-O-Meter Floor Scale. Maternal weight will be measured at each assessment.
- Maternal waist and hip measure: Measured with a flexible measurement tape and applied at the waist and hip levels.
- Infant weight measure: Measured with a portable Health-O-Meter Digital Infant Scale. Research staff will not touch the infant but arrange the scale to place the infant. Infant

weight will be measured before and after each breastfeeding observation in case of breastfeeding mothers to also measure the breast milk in the stomach.

- Infant length measure: Measured with Hopkins Measure Mat at home. Research staff will not touch the infant but arrange the measurement to place the infant.
- Saliva sample from mothers: Saliva samples in 3 collection tubes by Norgen Biotek Corporation will be used to collect maternal saliva samples by research staff.

Periodic assessments:

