All participants will be asked to engage in either phone-based or in-person periodic assessments. Assessments at 1-, 3-, and 6-month are phone assessment, and will be scheduled one week prior to monthly home visitation appointments. Assessments at 9- and 12-month are in-person at home. Interview questions include:

Questionnaires	Description	When administered
Breastfeeding motivation	How motivated to breastfeed for 6 and 12 months	Each assessment
Breastfeeding self-efficacy scale	How confident and knowledgeable you are in breastfeeding	Each assessment
Breastfeeding support	Type of social support for breastfeeding	Each assessment
Household structure	Total number of smokers living with the participant	Each assessment
Edinburgh postnatal depression scale	How depressed you feel	Each assessment
Sleep environment questionnaire	Sleep environment at home	1-month
Smoking cessation self-efficacy	Confidence of not smoking or maintaining abstinence	6-month
Brief infant sleep questionnaire	Infant sleep pattern	3-, 6-, 9-, and 12-month
Pittsburgh sleep quality index	How your sleep pattern is	3-, 6-, 9-, and 12-month
Barratt impulsivity scale	How impulsive you think you are	6- and 12-month
Daily log for pumping	Calendar on pumping patterns	9-, 12-month
Daily log for infant feeding	Calendar on feeding patterns	9-, 12-month
Breastfeeding barriers	Identified barriers to continue breastfeeding and solutions	9-, 12-month
Tobacco, alcohol, caffeine, marijuana use past 7-day	Recent use of licit substances	9-, 12-month
Menstrual cycle	Questions about the last menstrual period	9-, 12-month

Maternal/infant health survey	Recent medical events for moms and infants	9-, 12-month
Social constraints scale	People’s perception on social support	12-month
AUDIT-C	Recent alcohol use	12-month
TWEAK	Risk of maternal drinking	12-month
Participant satisfaction survey	How satisfied you are with the intervention	12-month
Holmes-Rahe life stress inventory	Stressful events that occurred in the last 12mos	12-month
Body uneasiness test	Body image concern	12-month
Employment	Employment situation and maternity leave	12-month
Infant behavior questionnaire	Behavior patterns and signs of your infant	12-month

- Breastfeeding observation (LATCH): Identify BF behavior: Audible swallowing, regular suck/swallow/breathe pattern, or visible milk in the infant's mouth. For pumping, observed pumping combined with observed resulting milk being fed to the infant at every in-person assessment.

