12.0 Withdrawal of Subjects

- 12.1** If women are incarcerated during 6 months of study participation, and if participants fail to attend scheduled visits during 6 months of study participation for more than 3 months, participants may

be subject to study withdrawal without their consent. Participants deemed eligible for study withdrawal by the PI will be informed of the decision by phone or mail.

Participants who were terminated on their study participation will not be followed up for periodic assessments or monthly home visitations. However, if participants need assistance in breastfeeding and other psychosocial issues, research staff provides referrals to appropriate community and hospital services.

13.0 Potential Benefits to Participants:

- 13.1** We believe that the aforementioned risks are reasonable in relation to the anticipated benefits to the mother and infant from continued BF. Participants receive direct benefits from participating in the study to increase access to existing breastfeeding support available in the community. Participants in the SC+BFI group may also experience increased motivation and confidence to continue breastfeeding for 6 months and beyond. In addition, the proposed project has the potential to provide important new scientific information regarding developing effective strategies for maintaining BF during 12 months. We believe the combined direct therapeutic benefits to subjects and new scientific information to be gained in the proposed studies outweigh any risks involved.

14.0 Financial Compensation:

- 14.1** There are three kinds of financial compensations involved in the study.
- 1) Contingent incentives on breastfeeding for participants in SC+BFI: This will be paid immediately and remotely on a Master Card as soon as breastfeeding is confirmed. The amount in the first month home visitation will be \$20, increasing by \$10 every month, for a total potential earning of \$270. Participants in this group will also be eligible to receive \$50 per selection of full breastfeeding food package at WIC at baseline, 3 months, and 6 months postpartum. Thus, a potential total earning in this group is \$420.
 - 2) Incentives on home visitations for participants in SC: This will be paid at the end of 6 months based on the number of completed home visitations. The amount per home visit will be \$40 for a total potential earning of \$240. This will be paid in form of retail gift cards.

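### In months 1–6 infant ER visits and medical events are asked about only at home visits whose pay depends on breastfeeding in one arm, so they could be under-recorded in SC+BFI

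*Combined protocol and SAP*

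**What the plan says.** **Outcome.** Section 4.2 hypothesises that the SC+BFI "condition will have significantly lower infant weight gain and incidents of ER visits for infants at 3-month postpartum".

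**Where infant events are asked.** In section 10.7 the "Maternal/infant health survey" is described as "Recent medical events for moms and infants". It is listed at the baseline home assessment and at the monthly home visitations. In the periodic-assessment table it appears at 9 and 12 months only. The same section states: "Assessments at 1-, 3-, and 6-month are phone assessment, and will be scheduled one week prior to monthly home visitation appointments". The calls therefore take place but do not carry the survey. On other sources, section 10.6 says: "Data source includes validated instruments for interview questions, breastfeeding observation records, and biological data and samples".

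**What a visit pays.** Section 10.2 says "Standard Care + BFI receives compensations at every home visit appointment if they are breastfeeding". Section 10.3 adds: "If a participant misses an appointment or does not demonstrate BF, she will not receive the incentive". For SC, section 14.1 gives $40 per home visit: "This will be paid at the end of 6 months based on the number of completed home visitations". The $20 for each phone assessment is the same in both arms and is handed over at the next home visit (10.5, 14.1).

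**Missing data.** The missing-values paragraph of the statistical section gives a coding rule for breastfeeding status only. It gives none for ER visits. Under 12.1, mothers who miss visits for more than 3 months may be withdrawn and are then not followed.

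**The concern.** The record of infant events up to month 6 depends on attending a visit, and cash for attending depends on feeding status in one arm only. The SC+BFI mothers with least financial reason to attend are those who have weaned. On the protocol's own premise (5.1) that early cessation raises infant infections, their infants are the ones expected to have more ER visits. If those reports are lost more often in SC+BFI than in SC, the 3-month ER comparison and the adverse event counts by arm can favour SC+BFI even when the incentive does nothing for infant health. This is separate from the coding of missing breastfeeding status, which affects the primary outcome.

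**Working it through.** **1. The plan's payment figures reproduce.**
- SC+BFI visit incentives: 20 + 30 + 40 + 50 + 60 + 70 = $270. With three $50 WIC bonuses: 270 + 150 = $420.
- SC: 6 × 40 = $240.

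**2. Visit-linked cash for a weaned mother.**
- Weaned before month 1: $0 in SC+BFI, $240 in SC.
- Weaned after month 3: $0 in SC+BFI, 3 × 40 = $120 in SC over the last three visits.
- Phone cards at months 1, 3 and 6: 3 × 20 = $60 in each arm. No card falls due at months 2, 4 and 5.

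**3. Possible size, with no true effect.**

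Inputs from the documents:
- ER rate 18% in both arms (pilot control figure at 3 months, 5.3).
- Weaned share *w* = 11% in the incentive arm by month 3 (pilot, 100% − 89% breastfeeding).

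Assumptions, because the documents give no figure for this trial:
- *w* could be as high as 30% or 50%.
- Attendance *a* of weaned SC+BFI mothers is 50–80%. Everyone else attends at 95%.
- A missing report is counted as no event.

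Formulas:
- Recorded rate in SC = 0.95 × 18% = 17.1%.
- Recorded rate in SC+BFI = 18% × [(1 − *w*) × 0.95 + *w* × *a*].
- Spurious difference = 18 × *w* × (0.95 − *a*) points.

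| *w* | *a* = 80% | *a* = 50% |
|---|---|---|
| 11% | 18 × 0.11 × 0.15 = 0.3 | 18 × 0.11 × 0.45 = 0.9 |
| 30% | 18 × 0.30 × 0.15 = 0.8 | 18 × 0.30 × 0.45 = 2.4 |
| 50% | 18 × 0.50 × 0.15 = 1.4 | 18 × 0.50 × 0.45 = 4.1 |

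**4. If only mothers who report are analysed.** The bias is zero when ER risk is unrelated to weaning. Suppose instead that weaned infants have twice the risk, with 18% overall. The rate while breastfeeding is *p* = 18% / [(1 − *w*) + 2*w*], and the recorded SC+BFI rate is [(1 − *w*) × 0.95 × *p* + *w* × *a* × 2*p*] / [(1 − *w*) × 0.95 + *w* × *a*].
- *w* = 50%, *p* = 12%: 17.5% at *a* = 80% and 16.1% at *a* = 50%, which is 0.5 and 1.9 points too low.
- *w* = 11%, *p* = 16.2%: 17.7% and 17.2%, which is 0.3 and 0.8 points too low.

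**5. Sensitivity of the direction.** If SC attendance were 85%, SC would record 0.85 × 18 = 15.3%. SC+BFI at *w* = 30% and *a* = 80% records (0.665 + 0.24) × 18 = 16.3%, so the sign reverses. With these inputs the bias favours SC+BFI only while SC attendance stays above 90.5%.

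**6. Against sampling error.** With 168 / 2 = 84 per arm and 18% ER, the standard error of the difference is √(2 × 0.18 × 0.82 / 84) = 5.9 points. Every figure above is below one standard error.

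**The case against.** A reader might infer that the visits pay a weaned SC+BFI mother nothing and that infant harm is under-recorded in that arm as a matter of fact. The documents do not support either statement.

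- **She is not left with nothing.** Diapers and wipes come with every home visit. They are written under SC, but 10.3 carries the remaining SC procedures over to SC+BFI. She also collects a $20 card at the month 3 visit, the time point of the ER hypothesis. Section 11.1 pays SC+BFI mothers who refuse observation on the same basis as controls, which sits uneasily with 10.3.
- **The SC payment is deferred.** It is a lump sum after month 6, collected at a university office (10.5), so it is a weaker pull to any one visit than $40 in hand.
- **Missed visits are chased.** There is a one-week make-up and, after three failed phone attempts, an unannounced home visit (10.3).
- **The pilot shows no attendance gap.** It also paid only on observed breastfeeding, and 100% of the incentive arm completed all assessments against 94% of controls (5.3).
- **Other routes may exist.** Adverse outcomes that a mother reports during the study are documented (10.3), infant medical care costs are to be tracked (3.1), and the wording of 10.6 need not be exhaustive.

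Most of this stands, and it limits the claim to a risk of unknown and probably small size. It does not remove the risk. The diapers and card are equal across arms and leave the $40 difference in place. The unannounced visit is triggered by failure to reach the mother, not by her declining. Adverse event reporting is spontaneous rather than a scheduled question. No source is named for medical costs. The pilot figure counts assessments completed in person, without saying how they were paid, in an arm where only 11% had weaned by month 3.

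**Conclusion.** The design allows capture of infant events to differ by arm. Infant ER visits and adverse events could be under-recorded in SC+BFI, probably toward the hypothesis. The amount is about 0.3–0.9 points at the pilot's weaned share and up to about 4 points at 50% weaned.

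Those sizes rest on the assumed 50–80% attendance of weaned mothers, 95% attendance elsewhere, an 18% ER rate in both arms, and a missing report being read as no event, which the plan does not state. The bias is nil if weaned mothers attend as well as others. It is also nil if only reporters are analysed and ER risk is unrelated to weaning. The direction would reverse if SC attendance were clearly lower than that of breastfeeding SC+BFI mothers.

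This bears on a secondary outcome and on adverse event counts, not on the primary endpoint. It is worth correcting because the remedy is cheap and unrecorded events cannot be reliably recovered later.

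**What to change.** 1. Add the existing Maternal/infant health survey to the 1-, 3- and 6-month phone assessments in both arms, with a fixed recall window: since birth at month 1, then since the last completed phone assessment.
2. Make that report the main source for the ER-visit outcome and for adverse event counts by arm. The call is paid equally in both arms and takes place before the home visit. Keep the home-visit survey as a supplement.
3. Report home-visit attendance by arm and feeding status.
4. State in the analysis plan that a missing ER report is not counted as no event, and how it will be handled.
5. Reconcile 10.3 and 11.1 on what an SC+BFI mother who does not demonstrate breastfeeding is paid.

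**Cost.** A few more minutes on three calls that already take place, and a protocol wording change. The data remain self-reported, as they are at the home visit. Mothers withdrawn for missed visits under 12.1 would still be lost, so the change reduces the problem without removing it.

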9.5 Study Endpoints

The primary outcome is the BF continuation rate at 6-month postpartum. This is determined by observed breastfeeding which includes: audible swallowing, regular suck/swallow/breath patters, visible milk in the infant's mouth after the infant is not latched anymore. Or, in the case of pumping moms, pumped milk and successful feeding to the infant. We hypothesize that the isolated effect of monthly incentives contingent on BF in SC+BFI will increase BF rates by 25% at 6-month compared to SC.

The exploratory outcome is the BF continuation rate at 12-month postpartum. We will hypothesize that SC+BFI will increase the BF rate at 12-month, compared to SC.

10.0 Study Procedures Involved:

- 10.1 We will use a randomized, two-group design (Standard Care+Breastfeeding Support vs. Standard Care+Breastfeeding Incentives).
- 10.2 We will use a permuted block random assignment (with block size = 6), assigning participants to one of 2 groups: *Standard Care* or *Standard Care + BFI*. This will allow us to keep group sizes approximately equivalent during the study maintaining an approximately equal size for the 2 groups. We will use propensity score matching to randomize the participants based on study site, as well as Black race and Puerto Rican ethnicity to maximize internal validity.

Allocation to study groups in randomization will be administered by [name] (Co-I) who will not have access to collected data until the end of the study. [name] will generate computer-

generated random numbers and keeps the original sequence in a password-protected electronic file that no other research staff can access. [name] will program the list of random numbers into an electronic file on RedCap which will automatically assign each participant to either condition. Other research staff can only view the result of randomization so that the allocation process remains concealed.

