Home-based support and problem-solving component: Blinded RA will also provide individual support and problem-solving in addition to WIC services. At each monthly home visit, blinded RA will ask participants to demonstrate BF, praise participants' efforts to continue BF, problem-solve issues around BF, provide local BF resources, and identify any issues with BF and other medical and psychosocial needs. Signs to verify ongoing BF include audible swallowing of breastmilk, regular suck/swallow/breathing patterns, visible milk in an infant's mouth, and (in case of pumping moms) pumped milk and successful feeding of an infant. When a participant has trouble with BF, she will be referred to a certified lactation consultant (CLC). Should a participant report any adverse maternal and infant outcome during the study period, blinded RA will document the event, report to the PI and IRBs, and make referrals as needed. Participants in SC will be asked to monitor their nutritional habit each month and to complete 24-hour recalls for each month. Research staff will mark a tally on a checklist at each monthly visit, and completion of nutritional monitoring will lead to a lump sum compensation for a total potential earning of \$240 with \$40 per completed monthly nutritional monitoring. Participants will also receive diapers and wipes at every home visit. This is comparable to the SC+BFI group to control for the incentive amount. However, in SC, this payment is tied to monitoring the nutritional habit and paid in a lump sum— not to observed BF at each month as in the SC+BFI group.

If a participant misses an appointment, this will be counted as incompliance with monthly nutritional monitoring. The participant will be given an opportunity to make up for the missed appointment within one-week timeframe from a due date. Blinded RA will contact a participant a week prior to the due date and make an appointment. After 3 attempts to reach a participant by

phone, blinded RA will provide a daytime unannounced home visit. Participants will be informed of potential unannounced home visits during study consent.

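### The research assistant who scores the primary outcome is called blinded, but the allocation-access rule as written contradicts this and no stated procedure secures it

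*Combined protocol and SAP*

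**What the plan says.** The primary outcome is breastfeeding at 6 months postpartum by direct observation. Section 9.5: "This is determined by observed breastfeeding which includes: audible swallowing, regular suck/swallow/breath patters, visible milk in the infant's mouth". Pumped milk fed successfully to the infant also counts.

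The observer is the RA on the monthly home visit. Section 10.3 introduces the home-based component with: "Blinded RA will also provide individual support and problem-solving". It says for SC: "At each monthly home visit, blinded RA will ask participants to demonstrate BF, praise participants' efforts to continue BF, problem-solve issues around BF". For SC+BFI it says: "Blinded RA will ask participants to demonstrate BF and provide individual support to praise efforts to continue BF and problem-solve BF issues". The RA is called blinded in both.

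On access to allocation, section 10.2 has REDCap assign the arm and adds: "Other research staff can only view the result of randomization so that the allocation process remains concealed".

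On visit content, section 10.3 says: "Participants in SC will be asked to monitor their nutritional habit each month and to complete 24-hour recalls for each month". It continues: "Research staff will mark a tally on a checklist at each monthly visit".

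On payment, sections 10.5 and 14.2 have an unblinded Project Coordinator load the SC+BFI cards remotely. Section 10.5 has unblinded staff tell SC mothers that their lump sum is ready.

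**The concern.** Concealing the sequence before assignment is not the same as hiding the arm afterwards. Section 10.2 achieves the first. It also tells research staff the second, and the RA who judges the feed appears to be one of them. The same RA praises the mother and helps her to continue. In SC+BFI, a positive call releases money at once. An observer who knows the arm has a reason to credit a doubtful feed there and none in SC.

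At stake are a possible bias toward SC+BFI in the primary comparison, and a trial report that claims blinded assessment without a protocol that supports it.

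**Working it through.** The plan gives no figure on this point, so there is none to reproduce. The check is a comparison of passages, followed by an illustration of size.

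**Does the visiting RA have access to the arm?**

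1. Section 10.2 allows other research staff to see the randomisation result and makes no exception for RAs.
2. Section 11.1 uses the term research staff for those who observe breastfeeding, and says research staff enter most data directly into REDCap, the system that assigns the arm.
3. Section 16.2 lists research assistants among those who may access stored data.
4. No section withholds the arm from the visiting RA, asks mothers not to disclose it, provides a separate outcome assessor, or checks whether blinding held.

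**Does visit content reveal the arm?** The text is divided.

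- For SC-only monitoring: section 10.3 describes monitoring, recalls and the tally under SC, and contrasts the basis of SC pay with that of SC+BFI. Section 11.1 links monitoring pay to the control condition.
- Against: section 10.3, under SC+BFI, calls the contingent incentive the sole difference between arms and says that remaining procedures match SC. The monthly-visit list in section 10.7 includes a log of the mother's eating with no arm restriction.
- Left open: section 10.3 has research staff mark the tally without naming the blinded RA, and does not say who takes the 24-hour recall or where.

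SC-only monitoring is the better-supported reading, but it is not settled.

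**Illustration of size.** Inputs:

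- 168/2 = 84 mothers per arm (section 3.1).
- Two-sided level 0.022 at the 6-month look (SAP, interim analyses).
- The same true rate p in both arms, 20% to 45%. This is an assumption, because the power statement gives no control rate. Section 5.1 cites 20% for Delaware Medicaid-eligible mothers, and 34.4% and 45.7% statewide for Delaware and Pennsylvania.
- A share f of non-breastfeeding SC+BFI mothers scored as breastfeeding. This is an assumption; the documents give no misclassification rate.

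Recorded SC+BFI rate: q = p + (1 − p)f. Spurious difference: (1 − p)f. Extra mothers credited: 84(1 − p)f. At p = 20% and f = 5%, the difference is 0.80 × 0.05 = 4.0 points and the extra credits are 84 × 0.04 = 3.4 mothers. The rejection probability comes from exact enumeration of both binomials with a pooled z test.

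| f | Spurious difference (points) | Extra mothers credited | False-positive rate at 0.022 |
|---|---|---|---|
| 0 | 0 | 0 | 2.2% to 2.4% |
| 3% | 1.7 to 2.4 | 1.4 to 2.0 | about 3% |
| 5% | 2.8 to 4.0 | 2.3 to 3.4 | 3.4% to 5% |
| 10% | 5.5 to 8.0 | 4.6 to 6.7 | 6% to 14% |

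The larger values belong to p = 20%. For scale, if the hypothesised 25% increase means percentage points, the 10% case is 5.5/25 = 22% to 8.0/25 = 32% of it.

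**The case against.** The plan does separate roles. Blinded RAs make the visits, an unblinded coordinator loads cards remotely, and unblinded staff handle SC pay. The access sentence in section 10.2 is about concealing the sequence, and other research staff could mean only the unblinded ones. This stands against the inference that blinding is impossible in this design. It does not remove the contradiction. The sentence carries no such limit, the protocol elsewhere uses research staff for the observers, and remote payment restricts neither the allocation view nor the visit content.

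A reader might also infer that only SC mothers have a tally at the visit and that it discloses the arm to the RA. The documents do not settle this, for the reasons set out in the comparison above.

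Observer discretion is limited too. Section 10.7 requires a LATCH checklist and weighing of the infant before and after an observed feed. Section 22.3 requires training until observations agree across at least two participants. These make large values of f less plausible. They do not remove the judgement, and weight change is not a stated outcome criterion.

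Finally, f is applied to every non-breastfeeding SC+BFI mother. Those with missing status count as non-breastfeeding (SAP, missing values) and show no feed to credit. If only a share g shows a feed, the error rate among those observed is f/g. With g assumed to be one half, the three cases need 6%, 10% and 20%. This objection stands, and it is why the table is only an illustration.

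**Conclusion.** The concern holds as a contradiction with a plausible direction of bias. The RA who scores a partly subjective primary outcome is called blinded, the access rule as written gives research staff the arm, and nothing in the plan secures the blinding. Whether monitoring, recalls and the tally are SC-only is unresolved and must be reconciled.

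Bias toward SC+BFI is possible, not established. It needs both that the RA learns the arm and that doubtful feeds are then credited more readily in SC+BFI. The false-positive rates in the table rest on an assumed crediting share, an assumed range of true rates and no true effect. They show that a few mothers credited in one arm would matter. They do not estimate what will happen, and the documents do not support the stronger statement that this design cannot have blinded assessment.

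**What to change.** 1. In section 10.2, restrict the REDCap allocation view to the unblinded coordinator and the unblinded payment staff, and state that visiting RAs have no access. Bring section 16.2 into line.
2. Use the same nutritional log or recall and the same visit checklist in both arms, and reconcile sections 10.3, 10.7 and 11.1 accordingly. Let unblinded staff compute SC pay from completed-visit records, which is already the basis in sections 10.2, 10.5 and 14.1; the wording in 10.3 should follow. Do not move the recall to SC-only phone calls: that could mean 84 × 6 = 504 calls and would give SC contact that SC+BFI lacks.
3. Ask mothers at consent not to discuss payment with the visiting RA.
4. Have the RA record a guess of arm at month 6, and report it by arm.

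If this is not done, delete blinded throughout and report outcome assessment as open.

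The cost is a permission change, a small form burden in SC+BFI, one script line and one extra item. Blinding will stay imperfect, because mothers know their arm and may say so.
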